5.5.2 Data Collection and Follow-up for Withdrawn Subjects

Although subjects may be withdrawn prematurely from the study, follow-up will continue for all such subjects. Subjects withdrawn because of unacceptable adverse events will be followed-until resolution or stabilization of the adverse event. An attempt will be made to obtain survival information for all subjects for a period of at least 3 years following the time of registration or until death, whichever comes first. For more information, see section 11, study calendar. This will include attempts to contact subjects via telephone and by certified letter using information available to the investigators and the study team. When possible, at least two attempts will also be made to contact the subject's next of kin to obtain such information while observing relevant privacy laws, where applicable.

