7.2.4 Medications affecting the qTC interval

The risk for qTC prolongation in patients receiving treatment with MGCD516 has not been adequately characterized in humans. Therefore, use of medications known to prolong the QTc interval and pose a risk of Torsades are prohibited during treatment with MGCD516. The use of medications known to prolong the QTc and pose a conditional risk of Torsades should be used with caution. Please see Appendix 1 for a list of medications to be avoided and used with caution in this setting.

7.3 **Duration of Therapy**

Treatment with the study drug will continue until one of the following applies:

- Disease progression
- Intercurrent illness that prevents further administration of treatment
- Unacceptable adverse event
- Patient's decision to withdraw from the study
- General or specific changes in the patient's condition render the patient unacceptable for further treatment in the judgment of the investigator

Patients whose disease status remains complete response, partial response or stable disease may

continue on therapy indefinitely until one of the above conditions applies.

7.4 **Duration of Follow Up**

Patients who do not progress while on study treatment will be followed every 3 months after completion of study treatment for the first 12 months of follow up and then every 6 months for both survival and disease status until death or for a period of at least 3 years, whichever comes first. For patients who are taken off therapy due to progression, information on survival will also be collected every 3 months after completion of study treatment for the first 12 months of follow up and then every 6 months until death or for a period of at least 3 years, whichever comes first. Patients removed from study for unacceptable adverse events will also be followed for information on resolution or stabilization of the adverse event.

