11. STUDY CALENDAR

	Screening (1)	Cycle 1(9)		Cycle 2 (9)		Cycle 3 + (9)			End of study (8)		
		1	8	15	1	8	15	1	8	15	
Procedure											
Informed consent	X										
Medical history	X										
Pathology confirmation	X										
Physical examination and vital signs	X	X	X	X	X			X			X
Height and weight	X	X	X	X	X			X			X
ECOG performance status	X	X	X	X	X			X			X
Adverse event assessment	X	X	X	X	X			X			X
ECG (1)	X										X
Echocardiogram (1)	X							X			
CBC w/differential (1,3)	X	X	X	X	X			X			X
Comprehensive metabolic panel (1,3,4)	X	X	X	X	X			X			X
Thyroid function tests (1, 3, 11)	X							X			X
Lipase (1, 3, 11)	X							X			X
Serum or urine pregnancy test (1)	X										
Urinalysis (1)	X							X (10)			X
CT or MRI of chest, abdomen, pelvis (2)	X							X			X
Tumor specimen submitted for next generation sequencing (5)	X										
Fresh tumor biopsy for RPPA studies (6)	X			X							
Follow-up telephone contact (7)											X

- (1): History and physical, all laboratory studies, urinalysis and single EKG must be completed 14 days or less prior to registration, with the exception of the serum or urine pregnancy test, which must be performed 7 days or less prior to registration. The echocardiogram must be completed within 56 days of registration, unless there is clinical suspicion for a change in cardiac status since that time, in which case it should be repeated. An echocardiogram will be repeated at any point during week 1 of cycle 3. Protocol-specific screening procedures that are performed as part of standard of care and are within these specified timeframes may be used for screening purposes.
- (2) Baseline imaging can include either (a) CT, spiral CT or MRI, or (b) FDG-PET with diagnostic CT performed with IV and oral contrast and CT acquired with 5 mm or less slice thickness. Imaging studies used for baseline tumor measurements must be obtained 28 days or less prior to registration. Imaging studies performed as part of standard care and within this

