timeframe may be used for screening purposes. Imaging studies are performed every 2 cycles (6 weeks, 42 days) for the first 36 weeks of study treatment, and then every 3 cycles (9 weeks, 63 days) thereafter. Imaging studies may be performed +/- 5 days from the required date. In the event of dose delays/holds, imaging studies should still be obtained at the scheduled timepoints as determined from registration, without delays to account for the dose delays/holds. Confirmatory scans must be obtained at least 4 weeks after the documentation of an objective response as discussed in section 12. It is acceptable to perform confirmatory assessments at the next appointed evaluation per protocol. Response assessment should include assessment of all sites of disease and use the same imaging method as used at baseline whenever possible.

- (3) All laboratory studies may be performed +/- 3 days from the required date.
- (4) Comprehensive metabolic panel is to include albumin, alkaline phosphatase, total bilirubin, bicarbonate, blood urea nitrogen, calcium, chloride, creatinine, glucose, potassium, total protein, AST, ALT and sodium.
- (5) Applies to liposarcoma patients only: All patients will have their most recent available biopsy material submitted for next generation sequencing to assess for genetic alterations of MGCD516 targets. See section 13 for more information on sample collection, processing and analysis. In cases were institutional policy or availability of prior specimens preclude this analysis, these studies will not be performed for that patient.
- (6) Applies to liposarcoma patients only: A subset of 10 patients will undergo baseline and ontreatment tumor biopsies for RPPA studies. The first 10 patients with lesions amenable to biopsy who are enrolled to the study (beginning with the first patient enrolled in stage I) will undergo these biopsies. See section 13 for information on sample collection, processing and analysis. The baseline biopsy specimen will be obtained at any point between day -14 and the date of first treatment with the study drug (cycle 1, day 1) provided consent is obtained and the other eligibility criteria are met. The on-treatment biopsy specimen will be performed with a target timepoint of cycle 1 day 15 (with a window of cycle 1 days 15 through 20). Biopsies will be obtained from the site of disease. If the study fails in stage I and proceeds to the exploratory cohort, no further RPPA analyses will be performed.

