- (7) A post-study follow-up contact via telephone by research staff will be conducted every 3 months during the first year after the end of study participation, and then every 6 months thereafter. For patients who do not progress on study treatment, information is obtained on disease status, survival status, and new anti-cancer therapy received. For patients who do progress on treatment, information is obtained on survival status and new anti-cancer therapy received. Follow-up continues for at least 3 years as measured from the date of study registration or until death, whichever comes first.
- (8) The end-of-study visit must be scheduled 28 days after the last dose of study drug (+/- 7 days) and before starting any new anti-neoplastic therapy. Imaging studies are only performed at this time if they would otherwise be indicated by that patient's study calendar.
- (9) Clinical assessments will occur on days 1, 8 and 15 of cycle 1, and then on day 1 of all cycles

thereafter. Clinical assessments may occur +/- 3 days from the target date.

- (10) The urinalysis is repeated on cycle 3 day 1. If there is no evidence of proteinuria, the urinalysis need not be repeated in subsequent cycles. If microscopic testing shows evidence of proteinuria, the study should be repeated on day 1 of subsequent studies.
- (11) Thyroid function tests (TSH, reflexive free T4/free T3 if TSH is abnormal) and lipase should be performed at baseline, C3D1, every other cycle after C3D1 (i.e. C5D1, C7D1 etc.) and at end of treatment.

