15.4 Analysis of Secondary Endpoints

Adverse event rates: Adverse events will be recorded at each clinical visit and will be categorized according to NCI CTCAE version 4.0. Adverse event rates will be reported as counts and percentages per adverse event basis by grade.

Overall survival and progression free survival: Overall survival is defined as the time from the date of first treatment with study drug to the time of death from any cause or last follow-up if alive. Progression free survival is defined as the time from first treatment with the study drug to the earliest of either disease progression or death from any cause. Patients who are alive and progression free will be censored at the time of their last follow-up. The Kaplan-Meir method will be used to evaluate all time to event endpoints³⁹. Median overall survival and median progression free survival will be reported with 95% confidence intervals.

Response rate: Patient responses will be evaluated according to RECIST version 1.1 as described in section 12. The response rate is defined as the number of patients having a best objective tumor status of complete response or partial response lasting at least four weeks divided by the number of evaluable patients. The response rate will be reported with 95% confidence intervals.

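### Section 15.4 censors PFS at last follow-up rather than at the last tumour assessment, so unscanned time after treatment stops can count as progression-free and lift the tail of the curve

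*Combined protocol and SAP*

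**What the plan says.** Section 15.4 defines PFS from first treatment to progression or death and states: "Patients who are alive and progression free will be censored at the time of their last follow-up". It plans Kaplan-Meier estimation and adds: "Median overall survival and median progression free survival will be reported with 95% confidence intervals". Section 12.6 defines PFS without a censoring rule, and no other section substitutes the last tumour assessment. In the overall survival definition of Section 15.4, last follow-up is the vital-status date.

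Progression is judged by RECIST 1.1 (Section 12.1). The study calendar (Section 11, note 2) ties scans to time on treatment: "Imaging studies are performed every 2 cycles (6 weeks, 42 days) for the first 36 weeks of study treatment", and every 9 weeks after that. Note 8 adds imaging at the end-of-study visit only if a scan is due then anyway. Section 7.3 lets patients stop without progression, for example for an adverse event or intercurrent illness.

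After that, note 7 provides that "A post-study follow-up contact via telephone by research staff will be conducted every 3 months" in the first year, and Section 7.4 continues the contacts "then every 6 months for both survival and disease status until death or for a period of at least 3 years". The calls ask about disease status, survival and new anti-cancer therapy, but require no imaging. Section 12.4.3 asks that progression be documented objectively, even off treatment, after symptomatic deterioration.

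**The concern.** The event in PFS is observed by scan, but the censoring date is set by contact. A patient who stops early without progression and is not scanned again can remain in the risk set, counted as progression-free, until the last telephone contact. Progression that is missed in that interval, or dated late, can only push the Kaplan-Meier curve up, and the effect builds over time.

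PFS is a secondary endpoint (Sections 2.2.2 and 4.1) and also enters the exploratory log-rank comparison by genetic alteration (Section 15.5.2). With at most 29 liposarcoma patients, three or four such patients can make up most of a late plateau.

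**Working it through.** **The plan's own figures.** The documents give no design figure for PFS. The Simon design in Section 15.1 (continue with 3 or more of 13, success with 9 or more of 29, 20% versus 40%) was recomputed by exact binomial: type 1 error 0.0999, power 0.8565, type 2 error 1 - 0.8565 = 0.1435. These agree with the stated 0.10, 85% and 0.14. They rest on the binary 12-week endpoint, which the censoring rule does not enter.

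**Schedule arithmetic.** Take a patient who stops for good on day 70.
- The end-of-study visit is 28 ± 7 days later: days 91 to 105.
- The week-12 scan is due on day 84, and "Imaging studies may be performed +/- 5 days from the required date": days 79 to 89.
- The windows do not meet, so the last scan is day 42 (1.4 months). If still called progression-free at 3 years, the patient is censored at 36 months.
- A stop on day d does get the week-12 scan if d + 35 ≥ 79 and d + 21 ≤ 89, that is, on days 44 to 68.

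**Worked example, n = 29 (illustrative data).** Twenty-five patients progress at scans: 7, 6, 4, 3, 2, 1, 1 and 1 at weeks 6, 12, 18, 24, 30, 36, 45 and 54. Four stop without progression, one after each of the 6-, 12-, 18- and 24-week scans, and are known alive by telephone to week 104.
- Censored at last scan, 52-week PFS = 22/29 × 15/21 × 10/14 × 6/9 × 3/5 × 2/3 × 1/2 = 0.052.
- Censored at last follow-up, nobody leaves the risk set before week 52, so PFS = 5/29 = 0.172.
- At 12 weeks the values are 0.542 and 16/29 = 0.552. The median is 18 weeks under both rules.

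**Simulation.** From the documents: the scan and call schedules, the end-of-study scan when one is due, and 36 months' follow-up. Assumed, because the documents do not give them: exponential time to progression, median 3 months; exponential survival after progression, median 12 months; 5%, 12% or 25% of patients stopping before progression, at a time uniform on 0.7 to 4.2 months; log-log confidence limits (Section 15.4 names no method). Truth is PFS had scans continued on schedule: 27.9% at 6 months and 9.0% at 12 months, with standard errors of 8.3 and 5.3 points at n = 29. Ranges run from all to none of the later progressions being reported at calls. The fix means censoring at the last scan, with reported progressions and deaths kept as events.

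| Stop before progression | Patients of 29 | 6-month PFS, plan | 12-month PFS, plan | Trials with median higher under plan than fix | Trials with median's upper 95% limit higher |
|---|---|---|---|---|---|
| 5% | 1.5 | 28.4-29.8% | 8.9-11.6% | 0-1.5% | 0-4.5% |
| 12% | 3.5 | 29.3-32.4% | 9.0-15.2% | 0-4.2% | 0.1-12.7% |
| 25% | 7 | 30.8-37.3% | 9.1-21.9% | 0.1-11.7% | 0.2-34.7% |

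The large-sample median is 4.14 months in every scenario. At 12% stopping with none reported, the mean sample median is 3.75 months (truth), 3.92 (plan) and 3.87 (fix); the mean upper limit is 5.57, 6.30 and 6.12.

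**How much the fix removes (12% stopping, 12-month PFS).**
- None reported, 36 months' follow-up: plan 15.2%, fix 13.6%, truth 9.0%. Share removed: 1.6/6.2, about a quarter.
- None reported, 12 to 24 months' follow-up (close to the timetable in Section 15.2): 15.1%, 10.2%, 9.0%. Share removed: 4.9/6.1, about 80%.
- Half reported, 36 months: plan 12.1%, fix 11.3%.
- All reported, 36 months: plan and fix agree within 0.1 point.

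**Sensitivity (12% stopping, none reported).** With median time to progression of 2, 3 or 5 months and median post-progression survival of 6, 12 or 24 months, plan minus truth at 12 months is 3.7 to 7.9 points. The fix removes 6-56% of it at 36 months and 58-96% at 12 to 24 months. The fix was never above the plan's rule.

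**The case against.** Six points can be made for the plan.

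- **Most of the excess has another cause.** At 36 months with none reported, about three quarters of the gap to truth comes from late deaths counted as events, which the fix keeps. At 12% stopping, about 18% of stoppers (0.6 of 29 patients) are still being censored at that point, or about 9% (0.3 patients) with half reported. This stands. With 12 to 24 months' follow-up, however, the censoring rule is the larger cause.
- **The calls ask for disease status**, so no progression surfacing in 3 years is an extreme case. This stands: it is the top of the range, and full reporting removes the difference at 36 months. But Section 15.4 requires no assessment behind a progression-free status.
- **Last follow-up might be read as the last disease evaluation.** That reading would remove the problem, but the text does not say so, and the overall survival definition uses the same term for vital status.
- **The day-70 example needs an immediate permanent stop.** True: during a dose hold the calendar keeps scans on schedule. Modelling a scan during the hold barely changed the curves.
- **The fix can run slightly low.** With full reporting and 12 to 24 months' follow-up it gives 8.4% at 12% stopping and 7.7% at 25%, against a true 9.0%. This stands.
- **Little listed output changes.** Section 15.4 lists the median and its interval, and the median seldom moves. This stands; the effect on the log-rank comparison was not estimated.

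**Conclusion.** The concern holds and is minor. Section 15.4 states a censoring rule that lets unscanned time count as progression-free, and the calendar makes such time likely for anyone who stops without progression. The direction is upward whenever later progression is reported incompletely. The effect is small at 12 weeks, larger in the tail, and usually absent from the median.

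The size depends on two quantities the documents do not give: how many patients stop before progression, and how fully the calls pick up later progression. At 12% stopping, the excess in 12-month PFS runs from none to about 6 points, roughly one standard error at n = 29. A separate simulation under other assumptions (true median 12 or 24 weeks, 20% or 40% stopping by 1 year) agreed in direction: with no later progression reported, the excess was 0.01 to 0.04 at 12 weeks and 0.04 to 0.11 at 52 weeks. Sample size, the 12-week progression-free rate and the Simon decision do not change.

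**What to change.** In Section 15.4, censor PFS for patients without documented progression or death at their last evaluable tumour assessment. Keep as events any progression documented after treatment stops and death from any cause. Use last follow-up for overall survival only. Report the present rule as one sensitivity analysis, together with the number of patients who stopped without progression, so that a reader can judge how far the tail depends on them.

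The cost is one sentence and one extra analysis. Scan dates are already collected, and no visit, scan or sample-size change is needed. A few patients will be censored earlier and reported PFS may be slightly lower. The report should not claim that the bias is gone: deaths long after the last scan still enter as late events.

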12.1.1 Definitions

Evaluable for toxicity: All patients will be evaluable for toxicity from the time of their first treatment with MGCD516.

Evaluable for objective response: Only those patients who have measurable disease present at baseline, have received at least one cycle of therapy, and have had their disease re-evaluated will be considered evaluable for response. These patients will have their response classified according to the definitions stated below. (Note: Patients who exhibit objective disease progression prior to the end of cycle 1 will also be considered evaluable.)

Evaluable Non-Target Disease Response: Patients who have lesions present at baseline that are evaluable but do not meet the definitions of measurable disease, have received at least one cycle of therapy, and have had their disease re-evaluated will be considered evaluable for non-target disease. The response assessment is based on the presence, absence, or unequivocal progression of the lesions.

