12.4.3 Evaluation of Best Overall Response

The best overall response is the best response recorded from the start of the treatment until disease progression/recurrence (taking as reference for progressive disease the smallest measurements recorded since the treatment started). The patient's best response assignment will depend on the achievement of both measurement and confirmation criteria.

Target Lesions	Non-Target Lesions	New Lesions	Overall Response	Best Overall Response when Confirmation is Required*
CR	CR	No	CR	≥4 wks.
				Confirmation**
CR	Non-CR/Non-PD	No	PR	
CR	Not evaluated	No	PR	≥4 wks.
PR	Non-CR/Non-PD/not	No	PR	Confirmation**
	evaluated			
SD	Non-CR/Non-PD/not	No	SD	documented at least
	evaluated			once ≥4 wks. from
				baseline**
PD	Any	Yes or	PD	
		No		
Any	PD***	Yes or	PD	no prior SD, PR or CR
		No		
Any	Any	Yes	PD	

^{*} See RECIST 1.1 manuscript for further details on what is evidence of a new lesion.

Note: Patients with a global deterioration of health status requiring discontinuation of treatment without objective evidence of disease progression at that time should be reported as "symptomatic deterioration." Every effort should be made to document the objective progression even after discontinuation of treatment.

12.5 **Duration of Response**

Duration of overall response: The duration of overall response is measured from the time measurement criteria are met for CR or PR (whichever is first recorded) until the first date that recurrent or progressive disease is objectively documented (taking as reference for progressive disease the smallest measurements recorded since the treatment started).

The duration of overall CR is measured from the time measurement criteria are first met for CR until the first date that progressive disease is objectively documented.

Duration of stable disease: Stable disease is measured from the start of the treatment until the criteria for progression are met, taking as reference the smallest measurements recorded since the treatment started, including the baseline measurements.

^{**} Only for non-randomized trials with response as primary endpoint.

^{***} In exceptional circumstances, unequivocal progression in non-target lesions may be accepted as disease progression.

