15.6.2 Evaluation of response

All patients included in the study who receive at least one treatment with the study drug will be assessed for response to treatment, even if there are major protocol deviations or if they are ultimately deemed ineligible. Each patient will be assigned one of the following categories: 1) complete response, 2) partial response, 3) stable disease, 4) progressive disease, 5) early death from malignant disease, 6) early death from toxicity, 7) early death from other cause, or 9) unknown (not assessable or insufficient data).

All of the patients who met the eligibility criteria, with the exception of those who received no study medication, will be included in the main analysis of the response rate. Patients in response categories 4-9 are considered to have a treatment failure. An incorrect treatment schedule or drug administration does not result in exclusion from the analysis of the response rate.

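### The response rate has two incompatible denominators: section 15.4 with 12.1.1 leaves out treated patients who have neither a re-evaluation nor documented early progression, while 15.6.2 counts them as failures

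*Combined protocol and SAP*

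**What the plan says.** **Section 15.4 (Analysis of Secondary Endpoints).** The numerator is patients whose best status is CR or PR sustained for four weeks. The rate is "complete response or partial response lasting at least four weeks divided by the number of evaluable patients", with a 95% confidence interval. For evaluation, 15.4 refers to section 12.

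**Section 12.1.1 (Definitions).** This is the only place that defines evaluable for objective response. Patients must have measurable disease at baseline, "have received at least one cycle of therapy, and have had their disease re-evaluated will be considered evaluable for response". There is one exception: "Patients who exhibit objective disease progression prior to the end of cycle 1 will also be considered evaluable".

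**Section 15.6.2 (Evaluation of response).** All eligible patients, "with the exception of those who received no study medication, will be included in the main analysis of the response rate". The categories include early death from disease, toxicity or another cause, and unknown status. The section adds: "Patients in response categories 4-9 are considered to have a treatment failure".

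**Confirmation.** Section 15.4 sets the four-week condition. The study calendar in section 11 supports it: "Confirmatory scans must be obtained at least 4 weeks after the documentation of an objective response". A double-asterisk footnote to the table in 12.4.3 reads "Only for non-randomized trials with response as primary endpoint". Response is a secondary endpoint here.

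**The concern.** One endpoint has two patient sets. Section 15.6.2 has a category for patients who could not be assessed so that they count as failures, and 12.1.1 removes the same patients. The affected group is narrow but realistic. A cycle lasts 21 days and the first scheduled scan comes at 6 weeks (section 11). A patient can therefore die, or stop for toxicity or decline, before any re-evaluation and without documented objective progression. Section 12.4.3 foresees symptomatic deterioration of this kind. Section 15.2 allows for non-evaluable patients separately from patients who never start treatment.

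At stake are the point estimate and interval of a named secondary efficacy endpoint in an open-label, single-arm trial. Two analysts could each cite the plan and report different rates, and the choice could be made after the data are known. The effect is larger in small groups. If stage 1 fails, 15.6.3 has the response rate reported separately for the liposarcoma patients (13) and the exploratory cohort (16).

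**Working it through.** **1. The plan's own figures.** The only design figures concern the primary endpoint, the progression-free rate at 12 weeks (section 15.1). These are 13 then 29 patients, continue with at least 3 successes, declare promising with at least 9, type 1 error 0.10, type 2 error 0.14 and power 85% for 20% versus 40%. The exact calculation is

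P(success | p) = sum over x = 3 to 13 of Bin(x; 13, p) × P(Bin(16, p) ≥ 9 - x).

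At p = 0.20 this gives 0.0999. At p = 0.40 it gives 0.8565, so the type 2 error is 0.1435. The stated figures reproduce. Response does not enter this rule, and the plan gives no target or power for the response rate.

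**2. Who is counted.** The table takes eligible patients who received at least one dose.

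| Patient | 15.4 with 12.1.1 | 15.6.2 main analysis |
|---|---|---|
| At least one cycle, re-evaluated | In | In |
| Objective progression before end of cycle 1 | In, non-responder | In, failure |
| Died or stopped, no re-evaluation, no such progression | **Out** | **In, failure** |

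Only the third row differs.

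**3. Direction and size.** Let n be the eligible treated patients, x the responders and m the patients in the third row. None of the m can be a responder, because none was re-evaluated. So

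- rate under 15.6.2 = x/n
- rate under 15.4 with 12.1.1 = x/(n - m)
- ratio = n/(n - m), which is at least 1.

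**4. Illustration.** The documents give neither x nor m, so both are assumptions. Intervals are exact (Clopper-Pearson) 95%.

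| m | 3 responders, n = 29 | 1 responder, n = 13 |
|---|---|---|
| 0 (the 15.6.2 rate) | 3/29 = 10.3% (2.2 to 27.4) | 1/13 = 7.7% (0.2 to 36.0) |
| 1 | 3/28 = 10.7% (2.3 to 28.2) | 1/12 = 8.3% (0.2 to 38.5) |
| 2 | 3/27 = 11.1% (2.4 to 29.2) | 1/11 = 9.1% (0.2 to 41.3) |
| 3 | 3/26 = 11.5% (2.4 to 30.2) | 1/10 = 10.0% (0.3 to 44.5) |

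At m = 2 the ratios are 29/27 = 1.07 and 13/11 = 1.18, or 0.8 and 1.4 percentage points.

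**5. With the replacements allowed in 15.2.** Up to 2 extra patients may be enrolled for non-evaluable patients and non-starters together. If both replace treated patients in the third row, the comparison is 3/31 = 9.7% (2.0 to 25.8) against 3/29 = 10.3% (2.2 to 27.4), or 0.7 points.

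**6. Confirmation.** An analyst who applies the 12.4.3 footnote when assigning best response must still meet the four-week condition in 15.4 before counting a responder. The numerator of the 15.4 rate does not change.

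**The case against.** The strongest reply is that the plan already settles the matter. Section 15.6.2 names its own set as the main analysis and says how failures are counted. Section 15.4 can be read as a summary that points to section 12 for RECIST assessment, not for a population. On that reading, one word in 15.4 is loose and no more. This has force and explains why the repair is small. It does not remove the conflict: 15.4 is where the endpoint is defined, it divides by evaluable patients, and 12.1.1 gives the only meaning of that term for response.

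The reply is also right that the effect is small. At the assumed m = 2 and n = 29, the shift is under one point against an interval about 25 points wide.

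Two stronger readings are tempting, and the documents do not support them.

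- **That all early failures are dropped.** A reader might infer this from the one-cycle requirement. Section 12.1.1 keeps patients with objective progression before the end of cycle 1, and 12.4.3 asks that progression be documented even after treatment stops.
- **That there are two competing confirmation rules, so unconfirmed responses could add 1/29 = 3.4 points each.** Section 15.4 sets the four-week condition itself, and sections 11, 12.1 and the text of 12.4.3 point the same way. The footnote is a stray general statement and cannot add responders to the 15.4 rate.

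**Conclusion.** The denominator conflict is real and in the current text. Using 15.4 with 12.1.1 biases the response rate upward by n/(n - m). For the assumed counts with m = 2, this is 10.3% to 11.1% at n = 29 and 7.7% to 9.1% at n = 13. These figures illustrate the size and do not predict it. Larger values of m would give larger shifts, but nothing in the documents supports a particular value.

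The direction rests on comparing the same eligible treated patients under both rules. Section 15.6.2 also has treated patients assessed "even if there are major protocol deviations or if they are ultimately deemed ineligible", while its main analysis is limited to eligible patients. A treated patient later found ineligible would be a separate difference between the sets, and its direction would depend on that patient's outcome.

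The consequence is limited. Response rate is secondary, has no decision rule, and leaves the Simon boundaries untouched. The correction is still worth making, because it fixes the denominator before results are known at almost no cost.

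**What to change.** 1. In 15.4, replace the evaluable-patient denominator with the main-analysis population of 15.6.2: all eligible patients who received at least one dose, with categories 4 to 9 as failures. The list in 15.6.2 has no category 8, so naming the failure categories would be clearer.
2. Report the rate in the 12.1.1 evaluable set, if wanted, only as a labelled supportive analysis.
3. As a minor consistency edit, state that the double-asterisk footnote in 12.4.3 does not waive the four-week requirement for CR and PR set in 15.4. Leave the stable-disease row as it is. That row carries the same marker, so a blanket confirmation statement in the footnote would wrongly attach to stable disease. This edit does not alter the response rate as 15.4 defines it.

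The cost is a few wording changes, with no new data and no change to sample size or the decision rule. The reported response rate may be slightly lower.
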